---

**The following Amendment(s) and Administrative Changes are included in this revised protocol:**

Amendment No.	Date of Amendment	Local Amendment No.	Date of local Amendment
1.0	27 August 2015	_____	_____
_____	_____	_____	_____
_____	_____	_____	_____
Administrative change No.	Date of Administrative Change	Local Administrative change No.	Date of local Administrative Change
_____	_____	_____	_____
_____	_____	_____	_____
_____	_____	_____	_____

## PROTOCOL SYNOPSIS

**A randomised, double-blind, double-dummy, parallel-group, multicenter, phase IIb study to evaluate the effect of ticagrelor 10 mg and 45 mg bid versus placebo in reducing the number of days with pain in young adults with sickle cell disease**

### Study site(s) and number of patients planned

This study will be conducted at approximately 32 centres in approximately 8 countries. It is expected that approximately 90 patients of both sexes, from 18 to 30 years of age (inclusive) will be randomised to study treatment.

Study period		Phase of development
Estimated date of first patient enrolled	Q2 2015	Phase IIb
Estimated date of last patient completed	Q3 2016	

### Study design

This is a randomised, double-blind, double-dummy, parallel-group, placebo-controlled, study evaluating 2 doses of ticagrelor in 90 patients aged 18 to 30 years, with sickle cell disease (SCD). Patients will start with a 4-week single-blind double-dummy placebo run-in period to determine the frequency of days with pain at baseline using an electronic diary (eDiary) every day. Approximately 180 patients will be enrolled for the run-in period in order to provide 90 patients meeting criteria for randomisation. Patients with  $\geq 4$  days of pain during last 4 weeks of the run-in period will be eligible for randomisation. Patients will then be randomised to double-blind double-dummy treatment period in a 1:1:1 ratio (30 to each treatment group) to receive ticagrelor 10 mg twice daily (bid), or 45 mg bid, or placebo bid for 12 weeks. Patient will be followed for safety assessment during and after 2 weeks of treatment completion.

During the 12 week treatment period, patients will complete a daily eDiary concerning daily pain intensity, pain location, use of analgesics and absence from school or work. At the end of the study patients will be asked to rate the change in their sickle cell pain compared to baseline. Platelet aggregation will be measured and reported as P2Y12 reaction units (PRU) pre-dose and 2 hours post-dose at the randomisation and 1 week post randomisation. Pharmacokinetic (PK) parameters will be measured at 2 hours post-dose at randomisation; and pre-dose and at 2 hours post-dose, 1 week post randomisation. Biomarkers will be assessed pre-dose at randomisation, at 1 week and 4 week post randomisation. During the study, patients will be evaluated for adverse events (AEs) including bleeding and vaso-occlusive crisis (VOC).

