#### 4. STUDY PLAN AND TIMING OF PROCEDURES

**Table 1 Study Plan Detailing the Procedures**

Study Period	Screening period	Treatment period				Follow-up period	For details see Protocol Section
Visit	Enrolment	Randomisation	Treat-ment	Treat-ment	End of treatment	Phone contact	
Visit Number	1	2	3	4 a	5	6	
Week	-4	0	1	4	12	14	
Day	-28	0	7	28	84	98	
Visit Window	-35 to -28	Not Applicable	±3 days	±7 days	±7 days	±7 days	
Signed and Dated Informed consent	✓						10.4
Inclusion/Exclusion Criteria	✓	✓ b					3.1 and 3.2
Allocation of E-code via IVRS/IWRS	✓						3.3
Randomisation via IVRS/IWRS		✓					3.3 and 3.5
Electronic Diary Assessment c : – Pain (worst/ average/ right now), daily – Analgesic use, daily – Absence school/ work, weekly – PGIC, end of treatment							5.1.1
Medical and Surgical History	✓						4.1
Demographics	✓						4.1
Vital Signs (BP and Pulse Rate)	✓	✓	✓	✓	✓		5.2.4
Weight and Height	✓				✓ d		5.2.4
Physical Examination	✓				✓		5.2.2
12-Lead ECG	✓						5.2.3
Ophthalmology examination (if not performed within previous 12 months)	✓						4.1

Study Period	Screening period	Treatment period				Follow-up period	For details see Protocol Section
Visit	Enrolment	Rando-misation	Treat-ment	Treat-ment	End of treatment	Phone contact	
Visit Number	1	2	3	4 a	5	6	
Week	-4	0	1	4	12	14	
Day	-28	0	7	28	84	98	
Visit Window	-35 to -28	Not Applicable	±3 days	±7 days	±7 days	±7 days	
Blood samples for Hematology and Clinical Chemistry	✓			✓	✓		5.2.1
Blood samples for coagulation (INR and PTT)	✓						5.2.1
Virology screen (HIV, HBsAg, and HCV)	✓						5.2.1
Urinalysis (dipstick)	✓			✓	✓		5.2.1
Pregnancy Test e	✓	✓		✓	✓		5.2.1
Platelet aggregation (PRU) (VerifyNow) f		✓	✓				5.5.1
Blood sampling for Biomarkers (optional)		✓ g	✓	✓			5.7
Blood sampling for Pharmacokinetics h		✓	✓				5.4
Dispense IP	✓ i	✓		✓			7
Administration of IP in Clinic	✓ i	✓	✓				7
Return IP and Drug Accountability		✓		✓	✓		7.5 and 7.6
Vaso-occlusive crisis	✓ j	✓	✓	✓	✓		5.1.2
Concomitant Medications	✓	✓	✓	✓	✓	✓	7.7
Adverse Event review (AEs and SAEs) including bleeding events	✓	✓	✓	✓	✓	✓	6

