AE adverse event; β-hCG beta-human chorionic gonadotropin; BP blood pressure; ECG electrocardiogram; HBsAg hepatitis B surface antigen; HCV hepatitis C virus; HIV human immunodeficiency virus; INR international normalized ratio; IVRS Interactive Voice Response System; IWRS Interactive Web Response System; IP investigational product; PTT Partial Thromboplastin Time; SAE serious adverse event.

a Patients should be contacted by telephone between Visits 4 and 5 (at Week 8 at a minimum), and Investigators are expected to follow subjects per local institutional guidelines during this period. If unscheduled visits are required for AEs or medical complications, please see Section 4.2.5.

b Confirm patient still meets inclusion and exclusion criteria prior to receiving first dose of study drug.

c Electronic diary will be dispensed to patient at Visit 1.

d Only weight will be measured.

- e For females of child bearing potential. At Screening (Visit 1), serum  $\beta$ -hCG; at all other visits, urine dipstick.
- f PRU will be assessed at 0 (pre-dose) and 2 hours post-dose at Visits 2 and 3.
- g Optional Biomarker sample needs to be collected only if patient agrees to consent for additional optional Biological Samples Research Addendum to Informed Consent Form. Blood sample must be taken prior to first dose of study drug at Visit 2.
- h PK will be measured 2 hours post-dose at Visit 2, and at 0 (pre-dose) and 2 hours post-dose at Visit 3.
- i At Screening, patients will be given matching placebo tablets for the 10 mg and 45 mg doses and starting at Visit 2, patients will be randomly assigned to 1 of 3 treatment regimens.
- j At Screening, history of VOC over previous 12 months will be recorded.

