### **4.2.1 Visit 2, Randomisation**

- Review and confirm inclusion/exclusion criteria for randomisation
- Patient eDiary will be collected from those who do not qualify for randomization
- Review concomitant medications and AEs including bleeding events
- Collect and assess compliance with run-in study drug based on tablet count
- Obtain vital signs (pulse rate and BP)
- Perform urine pregnancy test for females of child bearing potential
- Perform platelet aggregation measurement by using VerifyNow™ P2Y12 assay and reported as PRU (prior and 2 hours post-dose)
- Obtain specimens (blood) for biomarker analysis prior to study drug dispensing (only if patient agrees to consent for optional biomarker research)
- Contact IVRS/IWRS to randomise patient and obtain study drug dispensing bottles assignment number and dispense the study drug bottles
- Patient will be administered his/her first dose of the double-blind treatment at site
- A PK sample will be collected 2 hours post-dose

Schedule the Visit 3 date. Remind patient to bring eDiary in the next scheduled visit and instruct to not take their dose at home in the morning of Visit 3 and bring the study drug to clinic. After all the above assessments patients are allowed to leave the clinic.

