### **4.2.2 Visit 3, treatment visit**

- A PK sample will be collected 0 hr (pre-dose) and at 2 hours post-dose
- Review concomitant medications and AEs including bleeding events
- Obtain vital signs (pulse rate and BP)
- Perform platelet aggregation measurement by using VerifyNow™ P2Y12 assay and reported as PRU (prior and 2 hours post-dose)
- Obtain specimens (blood) for biomarker analysis

- Patient will be administered his/her Visit 3 morning dose at site

Schedule the Visit 4 date. Remind patient to bring eDiary and to return the unused study drug during their next scheduled visit.

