#### **4.2.3 Visit 4, treatment visit**

- Review concomitant medications and AEs including bleeding events
- Collect and assess compliance with study drug based on tablet count
- Obtain vital signs (pulse rate and BP)
- Obtain specimen for urinalysis and perform urine pregnancy test for females of child bearing potential
- Obtain specimens (blood) for safety laboratory panel and biomarker analysis
- Contact IVRS/IWRS to obtain study drug dispensing bottles assignment number and dispense the study drug bottles

Schedule the Visit 5 date. Remind patient to bring eDiary and to return the unused study drug during their next scheduled visit.

Patients should be contacted by telephone between Visits 4 and 5 (at Week 8 at a minimum), and Investigators are expected to follow subjects per local institutional guidelines during this period. If unscheduled visits are required for AEs or medical complications, please see Section [4.2.5](#).

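### The synopsis most naturally calls for pre-dose biomarker samples at Weeks 0, 1 and 4, but only the Visit 2 draw must be pre-dose, and Visit 4 has no home-dose hold

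*Protocol*

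**What the plan says.** The Study design paragraph of the protocol synopsis gives the biomarker timing in one sentence: "Biomarkers will be assessed pre-dose at randomisation, at 1 week and 4 week post randomisation".

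The operative text is more limited:

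- **Visit 2.** Footnote g of Table 1, attached to the Visit 2 biomarker tick alone, says "Blood sample must be taken prior to first dose of study drug at Visit 2". Section 4.2.1 agrees: "Obtain specimens (blood) for biomarker analysis prior to study drug dispensing".
- **Visit 3.** Before this visit sites must "instruct to not take their dose at home in the morning of Visit 3 and bring the study drug to clinic". The Visit 3 list times the PK sample ("A PK sample will be collected 0 hr (pre-dose) and at 2 hours post-dose") and times PRU in the same way. The biomarker sample has no timing. Section 7.2 places the Visit 3 dose after the 0-hour PRU and PK samples and does not mention biomarkers.
- **Visit 4.** The instruction given ahead of it is only "Schedule the Visit 4 date. Remind patient to bring eDiary and to return the unused study drug during their next scheduled visit". The visit list then says "Obtain specimens (blood) for safety laboratory panel and biomarker analysis", with no timing relative to dose. The Table 1 row "Administration of IP in Clinic" is ticked at Visits 1, 2 and 3, not at Visit 4.

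Section 5.7 makes the samples optional, says they may be analysed for sP-selectin, sCD40L and TXB2, and refers to Table 1 for collection. Section 2.4 lists change in these markers as an exploratory outcome.

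**The concern.** If the synopsis states the intent, the visit procedures do not deliver it at Week 4. A patient who has not been told otherwise will normally take the morning dose at home, attend Visit 4 and have blood drawn at whatever time the appointment falls.

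Time since dose matters in principle because the drug binds reversibly and is cleared within a dosing interval to a material extent. The protocol respects this for PRU, which belongs to the same exploratory objective as the biomarkers and is timed at 0 and 2 hours. If the markers respond to drug concentration, uneven time since dose adds scatter in the active arms. It also makes the Week 1 and Week 4 changes from baseline less comparable. What is at stake is how readable the Week 4 biomarker result is, and nothing beyond that.

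**Working it through.** The protocol states no figure that can be recomputed here. The check sets the visits side by side and then asks whether time since dose could plausibly matter.

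**Step 1. Rules by visit** (Table 1 and footnotes; sections 4.1, 4.2.1 to 4.2.3, 7.2)

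| Visit | Biomarker draw | Pre-dose draw required | Home dose held | Dose given in clinic |
|---|---|---|---|---|
| 2 (randomisation) | yes | yes | yes (4.1) | yes |
| 3 (Week 1) | yes | not stated | yes (4.2.1, 7.2) | yes |
| 4 (Week 4) | yes | not stated | no | no |

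A pre-dose draw is required at 1 of 3 visits and the home dose is held at 2 of 3. Visit 4 alone has neither.

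**Step 2. How the synopsis sentence reads.** It follows two other timing sentences. For PRU, one timing phrase covers both visits named after it. For PK, where timing differs by visit, the author separates the visits and restates the timing. The biomarker sentence has one timing word and no restatement, so it reads most like the PRU sentence, with pre-dose covering the whole list. The comma and the repeated preposition leave room for the narrower reading.

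**Step 3. Visit 3.** The dose is held at home and given on site after the 0-hour PRU and PK draws, whose actual times are recorded (5.4.1, 5.5.2). A biomarker sample at this visit is therefore either pre-dose or soon after a witnessed dose. The order of the list in 4.2.2 does not settle which, because its first item already includes a 2-hour post-dose sample.

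**Step 4. Visit 4.** Section 7.2 puts doses about 12 hours apart, so the theoretical range of time since dose is about 0 to 12 hours. Clinic hours will narrow it.

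**Step 5. Size of the concentration swing.** Section 1.1.3 gives a time to maximum of about 1.5 h and a half-life of about 7 h for ticagrelor, and 2.5 h and 8.6 h for the active metabolite. Assuming simple first-order decline after the peak, the fraction of peak left at 12 h is 2^(−(12 − t_max)/t_half):

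- ticagrelor: 2^(−(12 − 1.5)/7) = 2^(−1.5) = 0.35
- active metabolite: 2^(−(12 − 2.5)/8.6) = 2^(−1.105) = 0.47

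Concentration may thus vary roughly two- to threefold within a dosing interval. How far that carries through to the three markers cannot be computed from the protocol.

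**Step 6. Can time since dose be recovered afterwards?** Section 5.7 does not ask for the biomarker draw time. At Visit 4 it is available in practice, because safety blood is taken in the same step and its time is recorded under 5.2.1. Section 7.5 requires drug administration to be recorded but does not name the clock time of the last home dose. Recovery is possible in part, but not assured.

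**The case against.** The strongest reply is that nothing is contradicted. Where a sentence is open, the reading that fits the rest of the document should prevail. Footnote g and 4.2.1 confine the pre-dose rule to Visit 2, so the plan may simply intend one pre-treatment baseline and two on-treatment samples. Visit 4 has no PK, PRU or clinic dose, which is a coherent lighter visit. That reading is available, and a reader who infers a flat contradiction goes further than the text allows. Even so, it leaves the Week 4 time since dose uncontrolled.

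A reader might also infer that both on-treatment samples are uncontrolled. The documents do not support that. The hold and the witnessed dose largely control Visit 3, where only an explicit instruction is missing. Nor do counts of draws, blood volume or patients measure any harm.

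The Laboratory Manual is not shown, and section 9.2 has monitors check sample handling against it. It may set draw times. A home-dose hold, however, is an instruction to the patient, and this protocol puts such instructions in its own visit text for Visits 2 and 3.

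It is also fair to say that no effect of time since dose on these markers is shown. That stands and keeps the point minor.

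**Conclusion.** The point holds as a minor one. On its natural reading the synopsis asks for a Week 4 pre-dose biomarker sample that the visit procedures cannot reliably produce. On the narrower reading the document is consistent, but the Week 4 sample still has no fixed relation to dose. The operational gap is one visit; Visit 3 needs a clarifying line.

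The effect is confined to the precision of the on-treatment biomarker values and to how well Week 1 and Week 4 compare. A reader might infer a biased comparison with placebo. The documents do not support this: allocation is randomised and blinded, and every arm follows the same visit procedures. Section 8.5 names no Week 1 versus Week 4 biomarker comparison, and no primary, secondary or safety conclusion depends on these samples.

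The verdict assumes that patients without an instruction take their morning dose as usual, and that no unseen document adds a hold before Visit 4. The loss of precision cannot be quantified from the protocol.

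**What to change.** 1. In 4.2.2, tell patients who consented to biomarkers not to take the morning dose at home before Visit 4.
2. In 4.2.3, draw the biomarker sample before that dose, which the patient then takes from the newly dispensed bottles.
3. In 4.2.2, take the Visit 3 biomarker sample with the 0-hour PRU and PK samples, and extend the Visit 3 sentence in 7.2 to match.
4. Align footnote g of Table 1 so that it covers Visits 2, 3 and 4.
5. Record the time of the last dose and of the biomarker draw in the eCRF.

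If the sponsor does not want a hold before Visit 4, limit the pre-dose wording in the synopsis to Visit 2 and still record the last dose time at Visits 3 and 4.

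The cost is a few sentences, one or two eCRF fields and one slightly delayed morning dose for consenting patients. Under section 10.5 an amendment needs ethics approval and, where applicable, national authority approval, across about 32 centres in about 8 countries. The change does not justify an amendment of its own and can be bundled with the next one.

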## Objectives

Primary Objective:	Outcome Measure:
To investigate the efficacy of 2 different doses of ticagrelor versus placebo in reducing the number of days with pain due to SCD	Number of days with pain due to SCD

Secondary Objective:	Outcome Measure:
To determine the efficacy of 2 different doses of ticagrelor versus placebo in reducing the intensity of pain due to SCD	Intensity of pain due to SCD
To assess the efficacy of 2 different doses of ticagrelor versus placebo in reducing the use of analgesics due to SCD	Days of analgesic use

Safety Objective:	Outcome Measure:
To assess safety and tolerability of 2 different doses of ticagrelor versus placebo in patients with SCD	Number of major bleeding or clinically relevant non-major bleeding events AE/ Serious Adverse Events (SAEs) Vital signs, Laboratory Safety Samples

Exploratory Objective:	Outcome Measure:
To determine the efficacy of 2 different doses of ticagrelor versus placebo in reducing the frequency of VOC period in patients with SCD	Frequency of VOC
To assess the efficacy of 2 different doses of ticagrelor versus placebo in reducing the number of absent days from school/work in patients with SCD	Days absent from school/work
To assess the efficacy of 2 different doses of ticagrelor versus placebo in reducing the use of opioid analgesics in patients with SCD	Days of opioid analgesic use
To evaluate the pharmacokinetic (PK) properties of 2 doses of ticagrelor in young adult patients with SCD	Ticagrelor and active metabolite concentrations at Visits 2 and 3
To assess the effect of 2 different doses of ticagrelor on inhibition of platelet aggregation and biomarkers of platelet activation	PRU at 0 and 2 hours post-dose on Visits 2 and 3. Change in Soluble Platelet Selectin (sP-selectin), Soluble CD40 Ligand (sCD40L) and Thromboxane B2 (TXB2)

Exploratory Objective:	Outcome Measure:
To assess the dose-plasma concentration - response relationship with regards to PRU	The relationship between ticagrelor dose, plasma concentration and PRU using a population PK and Pharmacokinetic/Pharmacodynamic (PK/PD) modelling approach

### **Target patient population**

Patients eligible for this study include young adults aged  $\geq 18$  to  $\leq 30$  years of age (age at Visit 1) who are diagnosed with SCD [homozygous sickle cell (HbSS) or sickle beta-zero-thalassemia (HbS/ $\beta^0$ )]. Patients with  $\geq 4$  days of pain over the last 4 weeks of run-in period will be eligible for randomisation. Approximately 180 patients will enter the run-in period in order to provide 90 patients meeting criteria for randomisation.

### **Duration of treatment**

The study will start with a 4 week single-blind double-dummy placebo run-in period. Eligible patients will then be randomised in a 1:1:1 ratio (30 to each treatment group) to receive double-blind double-dummy ticagrelor 10 mg bid, 45 mg bid, or placebo bid for 12 weeks. Patients will be followed for 2 weeks safety assessment after 12 week study treatment period. The total expected study duration for an individual patient is approximately 18 weeks.

### **Investigational product, dosage and mode of administration**

- Ticagrelor 10 mg will be administered orally bid as a tablet
- Ticagrelor 45 mg will be administered orally bid as a tablet
- Matching Placebo for Ticagrelor 10 mg will be administered orally bid as a tablet
- Matching Placebo for Ticagrelor 45 mg will be administered orally bid as a tablet

### **Statistical methods**

No statistical comparisons are planned for the primary objective. PK, patient reported outcome (PRO) and safety measures will be summarized descriptively.

The number of days with pain due to SCD and the analysis of analgesic use due to SCD will be analysed using an ANCOVA model, with treatment, centre, baseline average value, as exploratory variables, and treatment as a fixed effect and centre as a random effect. Least squares differences in means between ticagrelor 45 mg and placebo and ticagrelor 10 mg and placebo with corresponding 90% confidence interval will be presented. The objectives will be analysed as a proportion of days, during the whole treatment period.

TABLE OF CONTENTS	PAGE
TITLE PAGE .....	1
PROTOCOL SYNOPSIS.....	2
TABLE OF CONTENTS.....	5
LIST OF ABBREVIATIONS AND DEFINITION OF TERMS .....	10
1. INTRODUCTION .....	13
1.1 Background and rationale for conducting this study .....	13
1.1.1 Disease under treatment.....	13
1.1.2 Study Drug.....	14
1.1.3 Pharmacokinetic Properties and Product Metabolism in Humans.....	14
1.2 Rationale for study design, doses and control groups.....	15
1.2.1 Overall rationale and study population .....	15
1.2.2 Study Design.....	15
1.2.3 Primary and secondary outcome measures .....	16
1.2.4 Dose and study duration.....	16
1.3 Benefit/risk and ethical assessment .....	16
1.4 Study Design.....	17
2. STUDY OBJECTIVES.....	18
2.1 Primary objective.....	18
2.2 Secondary objectives .....	18
2.3 Safety objectives .....	19
2.4 Exploratory objectives .....	19
3. PATIENT SELECTION, ENROLMENT, RANDOMISATION, RESTRICTIONS, DISCONTINUATION AND WITHDRAWAL.....	19
3.1 Inclusion criteria .....	20
3.2 Exclusion criteria .....	20
3.3 Patient enrolment and randomisation.....	22
3.4 Procedures for handling incorrectly enrolled or randomised patients .....	23
3.5 Methods for assigning treatment groups.....	23
3.6 Methods for ensuring blinding.....	24
3.7 Methods for unblinding.....	24
3.8 Restrictions .....	25

3.9	Discontinuation of investigational product.....	25
3.9.1	Procedures for discontinuation of a patient from IP .....	26
3.9.2	Procedure for management of dyspnea associated with investigational product .....	26
3.9.3	Procedure for management of elevated serum creatinine .....	26
3.9.4	Procedure for management of elevated liver function tests.....	26
3.10	Criteria for withdrawal.....	26
3.10.1	Screen failures.....	26
3.10.2	Withdrawal of the informed consent.....	27
